7.7.3 HCUA Activities at Six Months (T6)

The following sections outline the processes for how site staff communicate with providers at the six-month mark for each participant, including completion of the health care utilization survey (HCUS).

Site staff should still attempt to have the HCUS completed for any participant who at T6 has been identified as "lost to follow-up" or who dropped out of the study, **unless** the participant actively revoked their consent to participate in the study, **or** their consent to release medical records. Site staff cannot request HCUS completion for any participant who revokes these consents, and this should be recorded in the study MS Access database.

“Lost to follow-up” is defined as not completing follow-up activities after at least three no-shows to appointments during the participant’s follow-up window. For participants lost to follow-up at T6, site staff can again attempt to engage with them during their T12 follow-up windows.

7.7.3.1 Study participants who had an existing provider at baseline

Site staff will complete the same provider packet at T6 for participants in both the intervention and control groups who identified a provider at baseline.

The T6 provider packet for these participants includes:

- Provider Letter (*HCU Letter 4 - T6 Current Pt*)
- Copy of signed HIPAA form
- Copy of signed Medical Records Release Form
- HCUS (**Appendix Z**)

Site personnel will complete the first page of the HCUS prior to sending the provider communication packet, including the participant’s full name and date of birth so that the provider can verify that the participant data matches that reflected in the patient’s records. If the provider has no record of the patient, they will be instructed to return the face sheet to the RA. The RA will also need to write in the participant ID number in the designated box at the top of each remaining page of the survey.

The top portion of each page will include space to specify the range of service dates the HCUS is requesting. Study staff should enter the date the participant reaches T6 as the **end date** for the record request and the **start date** should be entered as the corresponding date 12 months earlier (which equates to the 6-month period that occurred just prior to the participant’s enrollment into the study). For example, if the participant reaches T6 in the study on November 1, 2016, the record request period will be identified as “November 1, 2015 through November 1, 2016.”

After filling out the relevant dates we are requesting data on the HCUS, please use a highlighter to highlight on the first page the text “Period of Requested Data: _____ to _____.” We want to emphasize these dates because they will be different compared to those specified on the Medical Records Release Form, which encompasses the entire span of the study and does not distinguish between the control and intervention groups.

All T6 provider packages should be faxed to or mailed to providers (based on individual processes outlined in each clinic’s MOU with the food bank site). We expect providers to return completed surveys via fax to the RA. Please see **section 7.7.7** for instructions on how to send completed provider surveys to the Urban Institute.

7.7.3.2 Study participants without provider at T0 but have provider at T6

For participants who did not have a provider at baseline (T0), but do identify having a provider at the six-month mark (T6), site staff will send the same T6 packet identified above to the participant’s new provider.

The T6 provider packet for these participants includes:

- Provider Letter (*HCU Letter 4 - T6 Current Pt*)
- Copy of signed HIPAA form
- Copy of signed Medical Records Release Form
- HCUS (**Appendix Z**)

The RA should follow the process outlined above for completing portions of the HCUS and sending the packet to providers.

7.7.3.3 Study participants without provider at T0 and who still do not have a provider at T6

For participants who did not have a provider at baseline (T0), and still do not identify having a provider at the six-month mark (T6), site staff will generate an active referral to a partner clinic per the process outlined in **section 3.2.1**.

In addition to the referral for care, site staff will send a modified T6 packet to the participant's new provider.

The T6 provider packet for these participants includes:

- Newly Referred Patient T6 Letter (*HCU Letter 5 - T6 Newly Referred Pt*)
- Copy of signed HIPAA form
- Copy of signed Medical Records Release Form
- HCUS (**Appendix Z**) – for use in the event the provider does have records for this participant

The RA should follow the process outlined above for completing portions of the HCUS and sending the packet to providers.

7.7.3.4 If a participant has switched providers between T0 and T6

It is possible that a participant may have switched primary care providers during the study intervention period. This could occur for several reasons: the participant may have moved and the prior provider location was no longer be convenient; the provider may have closed or changed the conditions under which it sees patients (e.g., the provider is no longer on the panel for the participant's insurance plan); the participant may have had a change in insurance or coverage status that affects his or her provider options; or the participant has decided to change for other reasons. It is important that the RA re-verify the primary care provider information for all participants at the six month survey point and note where any changes may have been made.

If there is more than one provider during the six-month period, then requests for records should be made to all primary care providers the participant has identified. Each provider will receive a T6 provider packet; however, the new provider should receive a modified version of the T6 letter that does not assume any prior communication with that provider (see: *HCU Letter 5 - T6 Newly Referred Pt*). The RA should make a note in the MS Access database that provider data is being requested from multiple providers. This information should be recorded on all survey forms for that participant

once they have been returned and logged into the database so that the analysis team is aware that two or more surveys will be entered for that period and special attention can be paid to reconciling the information for that participant.

7.7.4 HCUA Activities at Twelve Months (T12)

The following sections outline the processes for how site staff communicate with providers at the twelve-month mark for intervention group participants, including the completion of the second health care utilization survey (HCUS). These activities will be very similar to those conducted at T6. However, it is important to note that these activities will only be carried out for the intervention group. No further healthcare utilization activities will be conducted for the control group.

Site staff should still attempt to have the second HCUS completed for any INT participant who at T12 has been identified as “lost to follow-up” or who dropped out of the study, **unless** the participant actively revoked their consent to participate in the study, **or** their consent to release medical records. Site staff cannot request HCUS completion for any participant who revokes these consents, and this should be recorded in the study MS Access database.

“Lost to follow-up” is defined as not completing follow-up activities after at least three no-shows to appointments during the participant’s follow-up window. For participants lost to follow-up at T6, site staff can again attempt to engage with them during their T12 follow-up windows.

7.7.4.1 Intervention group participants that had an existing provider at T6

Site staff will complete a provider packet very similar to the packet outlined in 7.7.3.1.

The T12 provider packet for these participants includes:

- Provider Letter (*HCU Letter 7 – T12 Current Pt INT*)
- Copy of signed HIPAA form
- Copy of signed Medical Records Release Form
- HCUS (**Appendix Z**)

Site personnel will complete the first page of the HCUS prior to sending the provider communication packet, including the participant’s full name and date of birth so that the provider can verify that the participant data matches that reflected in the patient’s records. If the provider has no record of the patient, they will be instructed to return the face sheet to the RA. The RA will also need to write in the participant ID number in the designated box at the top of each remaining page of the survey.

The top portion of each page will include space to specify the range of service dates the HCUS is requesting. Study staff should enter the date the participant reaches T12 as the **end date** for the record request and the **start date** should be entered as the corresponding date 6 months earlier (which equates to the 6-month period after the participant completed the intervention). For example,

if the participant reaches T12 in the study on April 1, 2017, the record request period will be identified as “November 1, 2016 through May 1, 2017.”

After filling out the relevant dates we are requesting data on the HCUS, please use a highlighter to highlight on the first page the text “Period of Requested Data: _____ to _____.” We want to emphasize these dates because they will be different compared to those specified on the Medical Records Release Form, which encompasses the entire span of the study and does not distinguish between the control and intervention groups.

All T12 provider packages should be faxed to or mailed to providers (based on individual processes outlined in each clinic’s MOU with the food bank site). We expect providers to return completed surveys via fax to the RA. Please see **section 7.7.7** for instructions on how to send completed provider surveys to the Urban Institute.

7.7.4.2 Study participants without provider at T6 but have provider at T12

For participants who did not have a provider at six months (T6), but do identify having a provider at the twelve-month mark (T12), site staff will send the same T12 packet identified above to the participant’s new provider.

The T12 provider packet for these participants includes:

- Provider Letter (*HCU Letter 7 – T12 Current Pt*)
- Copy of signed HIPAA form
- Copy of signed Medical Records Release Form
- HCUS (**Appendix Z**)

The RA should follow the process outlined above for completing portions of the HCUS and sending the packet to providers.

7.7.4.3 Study participants without provider at T6 and who still do not have a provider at T12

For participants who do not have a provider at T12, site staff will generate an active referral to the partner clinic per the process outlined in **section 3.2.1**

In addition to the referral for care, site staff will send a modified T12 packet to the participant’s new provider for intervention group participants only.

The T12 provider packet for these participants includes:

- Newly Referred Patient T12 Letter (*HCU Letter 8 – T12 Newly Referred Pt*)
- Copy of signed HIPAA form
- Copy of signed Medical Records Release Form
- HCUS (**Appendix Z**) – for use if the provider does have records for this participant

The RA should follow the process outlined above for completing portions of the HCUS and sending the packet to providers.

7.7.4.4 If a participant has switched providers between T6 and T12

Follow directions as outlined in section 7.7.3.4. For new providers, staff should send providers the *HCU Letter 8 – T12 Newly Referred Pt.*

7.7.5 Sending Follow-Up Prompts to Primary Care Providers Regarding Survey

The RA should monitor the results of all provider record requests on a weekly basis. If there has been no response to a record request after two weeks, a reminder letter will be generated and sent to the provider (*HCU Letter 6 - Provider Survey Reminder*). This mailing will include a friendly reminder about the survey, and enclose another copy of the consent to release records and the survey. The RA will log the date of the follow-up mailing in the MS Access database. If there has been no response after two more weeks, the RA will generate one final written reminder with a copy of the survey and consent.

If there has been no response to the first and second written reminders after four weeks, the RA will implement a phone contact protocol. If the provider / clinic on file for the participant has an MOU with the FAITH-DM site, the RA will follow the contact procedures previously identified by the provider site. If there is no MOU, the RA will make up to three telephone attempts to talk to the practice manager or medical records department to inquire whether the survey has been received and/or if the survey was sent in error (e.g., the provider has no record of this patient). If there is patient data that matches the participant, the RA will encourage the provider to complete the survey, offer assistance as needed, and review the opportunity for financial incentives upon completion. If after three contacts that result in direct communication, the RA is still unsuccessful in obtaining a baseline survey, the RA will note the attempts and the lack of response in the MS Access database.

Outstanding record requests will be reviewed quarterly with Urban Institute staff and the FAITH-DM project manager to determine if the FAITH-DM team can provide any additional assistance in securing a response or if the case should be deemed “nonresponse.”

7.7.6 Financial Incentives for Provider Survey Completion

The FAITH-DM sites have funds allocated to provide reimbursement to providers for each survey completed (\$20). This information is included in the provider communication packet. Reimbursements should be generated quarterly by site personnel to ease the administrative burden for both the site personnel and providers (e.g., to avoid providers having to generate individual invoices for each record extraction).

7.7.7 Returning / Receiving the HCU survey

The provider communication packet will include instructions about how to return the survey to the site RA via fax. The site RA is responsible for logging receipt of a completed survey in the MS Access database. Similarly, provider requests for clarification on the survey or any follow-up prompts sent to the provider by the RA should be logged in the MS Access database so there is a complete picture of provider communication available to the site personnel. Once a quarter, the RA can tally the number of completed surveys by provider and generate the appropriate compensation from the food bank project funds, with a letter of thanks for their participation.

When the site RA receives the provider survey or any accompanying documentation the provider may have sent (e.g., printout of dates of service and diagnostic codes from their electronic health record), the RA must ensure that all PII must be removed before forwarding surveys to the Urban Institute.

This includes removing and shredding the provider face sheet with the personal data; making sure that the participant ID is included on the remaining survey pages but not associated with any PII (like name, date of birth, etc.) and blacking out the names or other identifying information from any attached records.

In lieu of the shredded provider face sheet, the RA should subsequently complete an Urban Institute HCUS Cover Sheet for the purpose of sending the survey to the Urban Institute (see **Appendix AX**). The cover sheet will ask for the participant ID, period of requested data, and date the survey was received, and will additionally include a space for any special notes or considerations about the survey that the RA wishes to communicate to the Urban Institute.

The RA should then make a copy of the survey / documentation with only the project identifier number displayed on each page and keep a copy for their files. At the end of every month, beginning with the month that provider surveys begin start arriving, the RA should assemble all completed provider surveys and send these in one mailing to the Urban Institute project contact via a verifiable, trackable delivery method, as described below. The UI project contact will provide the RA will email verification once the monthly survey package has been received and will verify the cost to the site of the mailing. Each quarter Urban Institute will generate a reimbursement check to the site for the costs of mailing the surveys.

Trackable Survey Delivery Methods

A trackable delivery method is defined as any mailing service that allows the sender to **confirm the receipt of your package** at the intended destination. Trackable delivery methods include:

- USPS Priority Mail with Delivery Confirmation
- USPS Priority Mail with Signature Confirmation
- USPS Express Mail (for overnight delivery requests) trackable delivery method
- Other trackable services such as UPS or FedEx that have delivery confirmation

Survey packages should be mailed to the following address:

Urban Institute
 Attn: [name]
 [name]
 [name]

See **Appendix BA** for detailed instructions when sending scanned, electronic HCUA data to the Urban Institute using encrypted USB devices.

7.7.8 Provider Packet Summary Table

The table below summarizes the different types of provider packets to be assembled at baseline and follow-up based upon the participant’s enrollment in the intervention or control group and their reporting of a PCP:

	Intervention group	Control group
Existing PCP	
At T0: HCU Letter 1 - T0 Current Pt INT, signed forms, information sheets
 
At T6: HCUS, HCU Letter 4 - T6 Current Pt, signed forms
 
At T12: HCUS, HCU Letter 7 – T12 Current Pt, signed forms
	
At T0: HCU Letter 3 - T0 Current Pt CONT, signed forms, information sheets
 
At T6: HCUS, HCU Letter 4 - T6 Current Pt, signed forms
 
At T12: No provider communication

No existing PCP (at T0)	
At T0: HCU Letter 2 - T0 Newly Referred Pt INT, signed forms, information sheets
 
At T6: HCUS, HCU Letter 4 - T6 Current Pt, signed forms
 
At T6: If participant still doesn't have PCP: HCU Letter 5 - T6 Newly Referred Pt, HCUS, signed forms, information sheets
	
At T0: No provider communication, but participant will be encouraged to see PCP
 
At T6: If participant now has PCP: HCUS, HCU Letter 4 - T6 Current Pt, signed forms, information sheets
 
At T6: If participant still doesn't have PCP: HCU Letter 5 - T6 Newly Referred Pt, HCUS, signed forms, information sheets

	
At T12: HCUS, HCU Letter 7 – T12 Current Pt, signed forms
 
At T12: If participant still doesn't have PCP: HCU Letter 8 – T12 Newly Referred Pt, HCUS, signed forms, information sheets
	
At T12: If participant now has a PCP, no provider communication
 
At T12: If participant still doesn't have PCP, use "Screening and Referral Form" to complete active referral

--	---	--

8 Randomization

In randomized, controlled clinical trials, participants are assigned to a treatment group based upon a pre-determined randomization scheme developed by the study statistician ([name], UCSF). Randomization is used to reduce bias in assignment to treatment. In our case, clients will be randomized to receive the intervention immediately or after a 6-month delay.

- **Randomization Plan:** We will use a 6-block randomization scheme to ensure that the rolling enrollment process across multiple food bank sites will distribute participants equally into each study arm over time. This scheme will be generated using the website www.randomization.com for each food bank site separately, which will create a list of the order of randomization by sequential participant ID.
- **Process Responsibilities:** UCSF will be in charge of creating the randomization scheme for each site. This will include generating the randomization list, preparing sealed envelopes by participant ID, and mailing them to each site to open as recruitment progresses. In the event a participant ID is not used (e.g., a client withdraws consent upon learning what group he/she is randomized to), site study staff should note the participant ID number, destroy the number and envelope, and report the event and ID number to UCSF. UCSF staff will determine if any adjustments need to be made to maintain balance between assignments to intervention and control groups, and will instruct study staff accordingly.

Participant Identification Numbers by Study Site	
Site	ID Numbers
Houston	101-399
Detroit	401-699
Oakland	701-999

- **Procedure for Randomizing a Participant:** The research assistant at each food bank will enroll participants into the study. No staff member will know the randomly selected allocation of the participant until the HbA1c screening, informed consent process, and baseline survey is completed. At the conclusion of this baseline visit, the staff member will open the sealed envelope that corresponds to the participant ID number of the enrolled client and determine the arm assignment, either immediate intervention or waitlist intervention.
- **Best Practices for Using Randomization Envelopes:** Study staff that participate in enrollment activities should use the following best practices to ensure consistency in the randomization process, and to foster a satisfactory client experience.
 - Have all of your enrollment materials available when you are meeting with a new participant (e.g., consent forms, education materials, survey materials, and randomization envelopes)
 - It is especially important to have the participant’s randomization envelope at your table (and in plain sight) during the entire enrollment process
 - Have only 1 randomization envelope at the table for each participant
 - In similar studies, some clients assigned to the waitlist control group have argued about their assignment, especially if the study staff leaves the area to retrieve the envelope after the consent and survey administration is completed (they may think staff selected the envelope based on their survey responses)
 - After the survey is completed, open the randomization envelope in front of the participant so they can observe the process

Randomization assignments must be documented in the Microsoft Access database.

9 Participant Timeline and Visit Schedule

A schedule of visits and evaluations that specifies what is to be done at each study phase and at each contact with the study participant is provided in **Appendix E**.

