5.2 Eligibility and Exclusion Criteria

Study eligibility is determined by a set of specific inclusion and exclusion criteria. Individuals must meet all eligibility criteria. This section defines the criteria, method for determination, and the specific forms needed to document eligibility.

Our specific inclusion criteria include:

- Type II diabetes mellitus with HbA1c $\geq 7.5\%$ using food bank point-of-care testing
- Food pantry client (defined as any individual engaging with a food bank or partner agency for food assistance, regardless if is their first visit or not, or if they are requesting direct food assistance, SNAP enrollment assistance, or general information on any food resources or programming)
- Reliable mode of contact (either phone or address) where they can be reached
- English or Spanish verbal fluency
- 18 years of age or older
- Intent to remain in the study area for at least the next 12 months
- Willingness to participate in intervention (including picking up bi-monthly food boxes and participating in diabetes education activities)

Exclusion criteria include:

- Type 1 diabetes
- Pregnant or less than 6 weeks post-partum*
- Cognitively impaired: dementia, mental illness, or active substance abuse severe enough to make client incapable of providing informed consent and could interfere with administration of the survey or participation in the intervention**
- Household member already enrolled in the study***

* Study participants who become pregnant after enrollment may remain in the study and participate in all study activities in their assigned group (intervention or control). Study staff will emphasize with any pregnant study participant the importance of staying connected with their healthcare providers (to receive regular pre-natal care and any pregnancy-specific diabetes self-management education and support).

** Refer to **Appendix AS** “Cognitive Impairment Assessment Tool” to assess cognitive impairment during participant enrollment; this form and process need only be used on clients where study staff suspect cognitive impairment.

*** Other household members with diabetes can share the food box, participate in the education, and have their HbA1c checked, but should not be enrolled in the study.

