	11b	If relevant, description of the similarity of interventions	<hr/>
Statistical methods	12a	Statistical methods used to compare groups for primary and secondary outcomes	<hr/>
	12b	Methods for additional analyses, such as subgroup analyses and adjusted analyses	<hr/>
Results			
Participant flow (a diagram is strongly recommended)	13a	For each group, the numbers of participants who were randomly assigned, received intended treatment, and were analysed for the primary outcome	<hr/>
	13b	For each group, losses and exclusions after randomisation, together with reasons	<hr/>
Recruitment	14a	Dates defining the periods of recruitment and follow-up	<hr/>
	14b	Why the trial ended or was stopped	<hr/>
Baseline data	15	A table showing baseline demographic and clinical characteristics for each group	<hr/>
Numbers analysed	16	For each group, number of participants (denominator) included in each analysis and whether the analysis was by original assigned groups	<hr/>
Outcomes and estimation	17a	For each primary and secondary outcome, results for each group, and the estimated effect size and its precision (such as 95% confidence interval)	<hr/>
	17b	For binary outcomes, presentation of both absolute and relative effect sizes is recommended	<hr/>
Ancillary analyses	18	Results of any other analyses performed, including subgroup analyses and adjusted analyses, distinguishing pre-specified from exploratory	<hr/>
Harms	19	All important harms or unintended effects in each group (for specific guidance see CONSORT for harms)	<hr/>
Discussion			
Limitations	20	Trial limitations, addressing sources of potential bias, imprecision, and, if relevant, multiplicity of analyses	<hr/>
Generalisability	21	Generalisability (external validity, applicability) of the trial findings	<hr/>

Interpretation	22	Interpretation consistent with results, balancing benefits and harms, and considering other relevant evidence	_____
----------------	----	---	-------

Other information

Registration	23	Registration number and name of trial registry	_____
--------------	----	--	-------

Protocol	24	Where the full trial protocol can be accessed, if available	_____
----------	----	---	-------

Funding	25	Sources of funding and other support (such as supply of drugs), role of funders	_____
---------	----	---	-------

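### Section 8 treats a client who withdraws after the envelope is opened as an unused ID, which may drop an already randomised person from the randomised denominator and the attrition test

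*Combined protocol and SAP*

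**What the plan says.** Section 8 (Randomization) of the combined protocol and SAP sets the order of events. HbA1c screening, consent and the baseline survey come first. Then: "At the conclusion of this baseline visit, the staff member will open the sealed envelope that corresponds to the participant ID number". The person is randomised when that envelope is opened.

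Under Process Responsibilities, the same section begins its rule for unused numbers: "In the event a participant ID is not used (e.g., a client withdraws consent upon learning what group he/she is randomized to". Site staff are to note the number, then "destroy the number and envelope, and report the event and ID number to UCSF". After that, "UCSF staff will determine if any adjustments need to be made to maintain balance between assignments to intervention and control groups", and sites are instructed accordingly. No rule for such adjustments is given.

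The best-practice list in section 8 records that "In similar studies, some clients assigned to the waitlist control group have argued about their assignment", particularly when staff leave to fetch the envelope.

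Section 13.4.4 defines the treatment indicator by assignment and calls its coefficient the intent-to-treat effect. If attrition does not differ by arm at the 5% level, no adjustment is made. If it does, Lee bounds are used, and the plan expects the higher loss in the control group. Multiple imputation is a sensitivity analysis. The section does not say whether clients who withdraw at the envelope count as randomised.

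The exclusion in section 5.2 that comes nearest to prior participation is "Household member already enrolled in the study". It says nothing of a client who was randomised before.

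**The concern.** An unused number should be one for which nobody was allocated. Section 7.6.2 has such a case: a client who does not get through enough of the baseline survey is never assigned, the number is not reused and the envelope is destroyed. Section 8 applies much the same disposal to someone whose allocation has been revealed.

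If data managers follow that label, the earliest losses after randomisation leave the denominator. These losses are likely to depend on arm: the trial is unblinded, the intervention group leaves the first visit with a food box, and section 13.4.4 itself expects more control loss. The attrition test would then be run on a set from which the most arm-driven losses had been removed, and that test alone decides whether bounds are computed. Adjusting later assignments in response to refusals would also depart from the pre-determined scheme described at the start of section 8.

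A secondary gap is that nothing in section 5.2 expressly bars a client who withdrew at the envelope from being screened and randomised again.

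**Working it through.** **Base figures.** Section 13.4.1 gives SDs of 1.6 and 1.9, correlation 0.51, a difference of 0.4, 90% power and two-sided alpha of 0.05. The adjusted SDs are 1.6 × √(1 − 0.51²) = 1.376 and 1.9 × √(1 − 0.51²) = 1.634. Then n = (1.376² + 1.634²) × (1.960 + 1.282)² / 0.4² = 299.8, so 300 per arm, as stated. The recruitment goal is 720, and equal allocation gives 360 per arm.

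**Assumptions that are not in the documents.** Refusals at the envelope occur among controls only, and 20% of everyone else is lost later in both arms. The 20% is the plan's overall attrition allowance. The refusal rate is varied.

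**Everyone whose envelope was opened is counted.** Intervention loss is 0.20 × 360 = 72. Control loss is refusals plus 20% of the remaining controls, rounded to whole people. The test is z = (difference in proportions) / √(p̄(1 − p̄) × 2/360), where p̄ is the pooled loss.

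| Control refusal | Refusals | Later control losses | Control loss of 360 | z against 72/360 | p |
|---|---|---|---|---|---|
| 5% | 18 | 0.20 × 342 = 68.4 | 86 (23.9%) | 1.26 | 0.21 |
| 8% | 29 | 0.20 × 331 = 66.2 | 95 (26.4%) | 2.03 | 0.042 |
| 10% | 36 | 0.20 × 324 = 64.8 | 101 (28.1%) | 2.53 | 0.011 |

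**Refusals treated as unused.** Control loss is 68/342, 66/331 or 65/324, which is 19.9%, 19.9% or 20.1%, against 20% in the intervention arm. The test finds nothing at any refusal rate.

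**Where the decision turns.** An excess of 22 control losses (94 against 72) gives z = 1.95 and p = 0.052. An excess of 23 (95 against 72) gives p = 0.042. The switch is therefore at about 8% control refusal under these assumptions. Refusals in the intervention arm would narrow the gap and raise that threshold.

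**What the switch does.** Lee bounds trim the arm with more follow-up by the relative difference in follow-up. At 10% refusal, follow-up is 288 intervention and 259 control, so (288 − 259)/288 = 10.1% of intervention outcomes are trimmed. At 8% it is (288 − 265)/288 = 8.0%. With refusers dropped from the count, follow-up is about 80% in both arms and there is essentially nothing to trim.

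**What does not move.** The ANCOVA in section 13.4.4 needs a follow-up value. Section 9.4 stops follow-up when consent is withdrawn, so these clients supply none. The complete-case estimate is the same whether they are called unused or lost.

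**The case against.** The strongest reply is that section 8 sets a rule for handling numbers and envelopes at sites and does not define an analysis set. Staff note the ID and report the event. UCSF generated the list by sequential ID and can look up the arm. Section 8 also requires assignments to be entered in Access, section 15.1 calls for reports of randomised group totals and disposition, and Appendix C intends every screened client to be traceable. The checklist in Appendix H asks for "For each group, losses and exclusions after randomisation, together with reasons", and the report to UCSF can supply that. Destroying the number may serve only to prevent its reuse. All of this stands, and it means the losses are recoverable. It does not supply a rule that keeps the person in the denominator, and section 13.4 is silent.

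Four stronger readings are tempting, and the documents do not support them:

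- **The rule biases the primary estimate.** Refusal by controls could bias a complete-case comparison, but it would do so under either label. Relabelling neither causes nor cures it.
- **Waitlist clients are known to withdraw more often.** The text says only that "some clients assigned to the waitlist control group have argued about their assignment", in similar studies, as the reason for a safeguard. Arguing is not withdrawing. Arm dependence is a reasonable expectation, and no rate is documented.
- **Later assignments stop being random.** UCSF is to decide whether any adjustment is needed, and the answer may be none. The fault is that the option is open and has no rule.
- **The plan permits a second draw.** No text allows it. The Appendix B log has a box for repeats, and the list of names, IDs and arms kept in Access (section 13.2) could catch a returning client. It is a gap in the eligibility criteria and not an authorised route.

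**Conclusion.** The point holds in limited form. Section 8 applies the category of unused ID to people who have been randomised. That sits badly with an effect defined by assignment and with a test of attrition by arm, and section 13.4 does not resolve it. Removal from the analysis denominator is the face-value reading of section 8, not something the plan states.

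The parts exposed are the attrition test, the Lee bounds, the set available for imputation, the flow counts and the integrity of the allocation sequence if adjustments are made. The complete-case primary estimate is not among them.

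The size is unknown because no refusal rate is given. Under the assumptions above, the label changes the attrition decision only when about 8% or more of controls refuse at the envelope. At 5% the test is non-significant even with everyone counted, though the randomised denominator would still be wrong. This should be fixed because the remedy is nearly free, but it does not undermine the primary comparison.

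**What to change.** In section 8, confine unused IDs to those whose envelope was never opened. Once an envelope is opened:

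- keep the ID and the assigned arm on record;
- retain the baseline data already collected, as far as consent allows;
- count the client as a post-randomisation loss in that arm in the section 13.4.4 attrition test, in the Lee bounds and in the Appendix C flow chart;
- make no rebalancing adjustment.

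Add a sentence to section 13.4.4 defining the randomised set as everyone whose envelope was opened.

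As a precaution, add previous randomisation in FAITH-DM to the section 5.2 exclusions and to the reasons for non-enrolment on the Appendix B screening log, checked against the list of names, IDs and arms in Access.

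The cost is a few sentences, one checkbox and a look-up at enrolment. Reported control attrition may be slightly higher, and the arm sizes may differ by a few people.
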